1.0 STUDY OBJECTIVE(S)

To evaluate the ocular safety, tolerability, and efficacy of topical administration of ISV-305 (0.1% dexamethasone in DuraSite[®] 2 ophthalmic solution) compared with DuraSite 2 Vehicle when dosed twice daily (BID) for 1 day prior to surgery, the day of surgery, and 14 days post cataract surgery.

2.0 STUDY DESIGN

This study is a Phase 3, randomized, multicenter, double-masked, vehicle-controlled, parallel-group clinical trial. Approximately 240 subjects will participate in the study and will be randomized in a 2:1 ratio to the ISV-305 group (160 subjects) and the vehicle group (80 subjects).

Written informed consent will be obtained from all subjects prior to any study-specific procedure. Subjects will be enrolled into a 16-day dosing phase, followed by a 2-week evaluation phase. There will be 7 visits scheduled during the study: a screening visit between 2 and 14 days prior to surgery; 3 visits during the dosing phase (Day 0 [Surgery Day], Day 1, and Day 8); and 3 visits during the evaluation phase (Day 15, Day 18, and Day 29). In addition, there will be a telephone call on Day -3 to remind subjects to begin dosing on Day -1, the day before surgery. Subjects will instill 3 doses prior to surgery (2 doses on Day -1, and 1 dose on Day 0 prior to surgery), 1 dose in the evening after surgery and continue dosing BID for 14 days after surgery.

Subjects will be randomized and receive instructions for dosing at home and completing a pain and dosing diary. Subjects will be cautioned to dose only for the specified amount of time. One bottle of investigational product (IP) will be dispensed to the subject, and a second bottle will remain at the site as a precaution only in the event of loss, etc., and will not be dispensed unless necessary. Throughout this protocol, the surgery eye is referred to as the study eye, and the fellow eye is referred to as the non-study eye.

All ratings and procedures should be performed by the same examiner from visit to visit whenever possible. Additional exams may be scheduled as necessary to ensure the safety of the subjects during the study period.

Subjects who terminate use of IP for any reason will be withdrawn from the study, the reason(s) clearly described on the subject's electronic Case Report Form (eCRF) and source documents, and the sponsor or designee will be notified.

If the investigator determines lack of efficacy during the dosing period, administration of a rescue medication (i.e., another medication to treat ocular inflammation and/or ocular pain in the surgery eye [study eye]) must occur after subject is withdrawn from the study, and be clearly documented on the source documents and the designated eCRF.

All adverse events (AEs), regardless of severity, will be followed throughout the study to the final study visit, until they resolve or resolve with sequelae (as judged by the investigator). Ongoing AEs will be followed beyond the final study visit at the discretion of the investigator and recorded in the source documents.

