6.0 CLINICAL ASSESSMENTS/PROCEDURES

6.1 Schedule of Assessments

The procedures and measurements to be evaluated at each study visit are shown in Table 1: Schedule of Assessments.

Table 1: Schedule of Assessments

Evaluation ¹	Screening/ Randomization Phase	Dosing Phase (16 Days)				Evaluation Phase (15 Days)		
	Visit 1 Day -14 to Day -2	Phone Call Day -3 (±1)	Visit 2 Day 0 (Day of Surgery)	Visit 3 Day 1 (+ 1)	Visit 4 Day 8 (± 1)	Visit 5 Day 15 (+1)	Visit 6 Day 18 (-1/+2)	Visit 7 Day 29 (± 2)
Written Informed Consent	X							
Demographics	X							
Entry Criteria	X							
Medical/Medication History	X							
Urine Pregnancy Test	X							X
Slit Lamp Biomicroscopy ²	X			X	X	X	X	X
Visual Analog Scale	X			X	X	X	X	X
Intraocular Pressure	X			X	X	X	X	X
Best Corrected Visual Acuity	X			X ³	X	X	X	X
Ophthalmoscopy ²	X					X	X ⁵	X ⁵
Confirm and Document Subject Eligibility	X							
Randomization	X							
Dispense IP and Pain/Dosing Diary	X							
Instruct Subject on IP and Dosing/Pain Diary	X							
AE Assessment	X	X	X	X	X	X	X	X
Dosing Reminder Call		X						
Update Concomitant Medications			X	X	X	X	X	X
Review Pain/Dosing Diary			X	X	X	X	X ⁴	X ⁵
Collect IP						X	X ⁵	X ⁵
Collect Pain/Dosing Diary							X	X ⁵
Exit Subject From Study								X

IP = Investigational Product; AE = adverse event; eCRF = electronic case report form

¹All eye exams are to be conducted in the study eye only. The fellow eye (non-study eye) may be examined at the investigators' discretion.

²Performed by a board-certified ophthalmologist.

³A pinhole test may be employed at Day 1 (Visit 3).

⁴Dosing terminates on Day 14. Pain is assessed through the evening of Day 17.

⁵If not completed at previous visit.

Note: Unscheduled visits may occur during the study period. All assessments will be recorded on the eCRF for unscheduled visits, but it is up to the investigator which assessments to conduct. If the subject exits early, all Visit 7 assessments should be conducted, including ophthalmoscopy if not obtained at Day 15 (Visit 5).

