## 5.0 ANALYSIS POPULATIONS

All efficacy endpoints will be analyzed using the modified intent-to-treat (mITT) population. The Per-Protocol (PP) population will be used for the analysis of the primary and secondary endpoints to examine the robustness of the primary analyses.

Safety and tolerability will be analyzed using the safety population.

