## **5.2 Modified Intent-To-Treat Population (mITT)**

The mITT population includes randomized subjects that undergo cataract surgery, receive at least one dose of IP, and have at least one post-surgery efficacy assessment. Subjects who receive rescue medications will be included in the mITT but will be treated as failures. This population will be used in all efficacy analyses. Subjects in the mITT population will be analyzed in the treatment group to which they were assigned by the randomization scheme, regardless of which IP if any, they receive.

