## **5.3 Per-Protocol Population (PP)**

The per protocol (PP) population includes all subjects in the mITT population excluding those subjects who receive rescue medications or have major protocol violations that may compromise their efficacy data.

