### 6.1.1 Definitions Relative to Efficacy Parameters

#### **Proportion of Subjects with ACC Grade 0 at a Given Time Point**

Proportion = Number of responders at Day X / Total number of subjects in the mITT population

Notes:

1. Responders are those subjects who had ACC grade of 0 either at Day X or the last assessment prior to Day X visit (in case the Day X was not completed).
2. Those subjects who received a rescue medication between and including Day 0 and X will be considered as treatment failure or non-responder, despite a subject with zero cell count either at Day X or the last assessment prior to Day X visit (in case the Day X was not completed).

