## **6.2 Handling of Missing Data and/or Invalid Data and Outliers**

### **6.2.1 Missing Data Analysis Methods for Efficacy Data**

The Last Observation Carried Forward (LOCF) method will be used to impute missing values for the primary and all secondary endpoints. In LOCF imputation, missing Day X values will be imputed using the last non-missing observation prior to Day X.

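### Stopping study drug ends study visits, so unrescued stoppers get a carried-forward grade as their primary result, and no planned analysis tests that imputation for the primary endpoint

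*Protocol*

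**What the plan says.** **Stopping drug.** Protocol 2.0: "Subjects who terminate use of IP for any reason will be withdrawn from the study". Rescue for lack of efficacy "must occur after subject is withdrawn from the study, and be clearly documented on the source documents and the designated eCRF".

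**After withdrawal.** The note to Table 1 in Protocol 6.1 asks for one examination: "If the subject exits early, all Visit 7 assessments should be conducted". Table 1 includes slit lamp at Visit 7, so ACC is graded at exit. Beyond that, Protocol 7.4 follows subjects withdrawn because of an AE or SAE until the event outcome is known. No efficacy visit is kept.

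**Primary result when Day 15 is missing.** SAP 6.2.1 applies LOCF to the primary and all secondary endpoints: "missing Day X values will be imputed using the last non-missing observation prior to Day X". SAP 6.1.1 and 7.4.2 let that earlier grade decide response. Anyone rescued from Day 0 through Day 15 is a failure whatever the grade. To enter the mITT population, a subject need only undergo surgery, take one dose and "have at least one post-surgery efficacy assessment" (SAP 5.2).

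**Checks.** SAP 7.4.3 assesses LOCF by multiple imputation, for the VAS pain endpoint only. SAP 7.4.2, on the primary endpoint, has no counterpart. SAP 5.0 says the per-protocol population "will be used for the analysis of the primary and secondary endpoints to examine the robustness of the primary analyses". SAP 5.3 excludes rescued subjects and those who "have major protocol violations that may compromise their efficacy data", without saying whether a missing Day 15 visit is such a violation.

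**The concern.** The endpoint is clearance of cells at Day 15. For an unrescued stopper, a grade from an earlier day stands in for it, although an already scheduled visit could have supplied the real one. The error can go either way. Cells at exit that clear by Day 15 understate that arm's response; a clear exit examination followed by recurrence overstates it.

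Similar errors in both arms largely cancel. Errors that differ between arms change the estimated treatment difference, and no analysis in the SAP would show it. The per-protocol analysis does not help: if a missing Day 15 counts as a major violation it drops the subject, and if not it reuses the same carried value.

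**Working it through.** **Inputs from the documents.** 160 ISV-305 and 80 vehicle subjects (Protocol 2.0); two-sided Z-test with pooled variance and continuity correction (SAP 7.4.2); alpha 0.05 (SAP 7.1). The documents supplied give no power, response rates or dropout rate, so there is no planning figure to reproduce.

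**Age of the carried grade.** At most 15 − 1 = 14 days if Day 1 is the last assessment, and 15 − 8 = 7 days if Day 8 is. An exit examination done as required will usually be more recent.

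**Assumptions.** 5% of each arm stop without rescue: 0.05 × 160 = 8 and 0.05 × 80 = 4. LOCF counts all of them as failures. The vehicle LOCF result is 24/80 (30%).

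**Test.** With pooled proportion p̄ = (x_A + x_V)/240,

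z = (|x_A/160 − x_V/80| − c) / √[p̄(1 − p̄)(1/160 + 1/80)], where c = 0.5 × (1/160 + 1/80) = 0.009375.

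For 72/160 v 24/80: difference 0.150, p̄ = 96/240 = 0.400, SE = 0.0671, z = (0.150 − 0.0094)/0.0671 = 2.096, p = 0.036.

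**Varying the stoppers' true outcomes.** If *a* of 8 ISV-305 and *b* of 4 vehicle stoppers were in fact clear at Day 15, the comparison becomes (x_A + a)/160 v (24 + b)/80. There are 9 × 5 = 45 combinations.

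| ISV-305 by LOCF | LOCF p | All stoppers clear (+8, +4) | Both arms shifted down (−8, −4) | Combinations with p ≥ 0.05 |
|---|---|---|---|---|
| 72/160 | 0.036 | 0.039 | 0.031 | 16 of 45 |
| 76/160 | 0.014 | 0.015 | 0.012 | 4 of 45 |
| 80/160 | 0.0050 | 0.0053 | 0.0042 | 0 |
| 88/160 | 0.0004 | 0.0004 | 0.0004 | 0 |

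These are counts of combinations, not probabilities. The downward shift is a separate case, in which stoppers carried as responders were not. Every combination that loses significance has a higher response rate in vehicle stoppers than in ISV-305 stoppers. Examples:

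- 72/160 with 2 of 8 v 2 of 4 clear: 74/160 v 26/80, p = 0.058.
- 76/160 with 0 of 8 v 3 of 4 clear: 76/160 v 27/80, p = 0.059.

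Equal rates (2 and 1, 4 and 2, 6 and 3, 8 and 4) stay below 0.05 in every row. If LOCF instead counts half the stoppers as responders (4 of 8 and 2 of 4), the counts are again 16, 4, 0 and 0.

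**Error in the other direction.** If 4 ISV-305 stoppers carried as responders were not, and vehicle is unchanged, 74/160 v 24/80 (p = 0.023) becomes 70/160 v 24/80 (p = 0.055).

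**Non-responder imputation.** Where LOCF already counts all stoppers as failures, this returns the LOCF result (0.036, 0.014), so it would reveal none of the losing combinations.

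**Unequal stopping.** Let 8 ISV-305 (5%) and 12 vehicle (15%) subjects stop, all carried as failures and all in fact clear. Then 80/160 v 24/80 (p = 0.005) becomes 88/160 v 36/80, p = 0.19. Here the stoppers' response rate is the same in both arms and the LOCF result was not close.

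**The case against.** **The informative dropouts are already handled.** Rescue covers any other medication for inflammation or pain in the study eye, must be recorded on the eCRF, and makes the subject a failure. This stands and limits the gap to unrescued stoppers, whose number is unknown; 5% is an assumption. One reservation is that rescue follows withdrawal, and no Day 15 contact is scheduled that would pick up later use.

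**The 14-day and 7-day figures are worst cases.** They are, because the exit examination normally supplies the carried grade. It is still not a Day 15 grade.

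**The effect is small.** With equal 5% stopping, no combination matters at 80/160 or above, and at 76/160 a loss needs at least 3 of 4 vehicle stoppers clear with at most 2 of 8 on ISV-305. The documents give no reason to expect vehicle stoppers to do better. That is fair for equal stopping. The unequal-stopping case shows that the limit comes from the assumption of equal stopping.

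**Withdrawals will be visible.** SAP 7.2 tabulates withdrawals with the primary reason by arm, and further analyses could be described in the study report. This shows how many left, not what their missing grades do to the result; an analysis added later would not be pre-specified.

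**Keeping stoppers in follow-up changes the quantity estimated.** This does not stand. SAP 7.4.2 already uses the Day 15 grade whenever that visit is completed.

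**Conclusion.** The concern holds, as an improvement of modest priority. The withdrawal rule removes a Day 15 result that could have been observed, LOCF fills it, and the SAP's only check on LOCF is for a secondary endpoint.

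Size and direction cannot be fixed from the documents. Under equal 5% stopping and vehicle at 24/80, the conclusion is at risk only when stoppers' outcomes differ between arms and the result is close: 16 of 45 combinations at 72/160, 4 at 76/160, none at 80/160 or 88/160. If vehicle subjects stop more often, a clear LOCF result can also be affected. The text of the plan supports the gap directly; its practical weight depends on how many subjects stop without rescue, and in which arm.

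**What to change.** **Protocol 2.0.** State that stopping study drug ends treatment only. Unless consent is withdrawn, stoppers attend the remaining scheduled visits, at minimum Day 15, with ACC, VAS, IOP, adverse events and concomitant and rescue medication recorded.

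**SAP 7.4.2.** Use the observed Day 15 ACC for unrescued stoppers and keep rescue through Day 15 as failure. Extend the multiple imputation of SAP 7.4.3 to the primary endpoint. Add a tipping-point analysis that varies the missing outcomes in both directions and separately in each arm. Non-responder imputation may be added but is not enough alone.

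**Cost.** One change to the withdrawal rule, two or three SAP sentences, and a few extra routine visits for stoppers. If enrolment is over, the imputation and tipping-point analyses can still be added before unmasking.

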3.0 STUDY POPULATION

Patients ≥ 17 years of age who are scheduled to undergo uncomplicated unilateral cataract surgery and who meet all study entry criteria. Approximately 240 subjects will be enrolled in the United States.

3.1 Inclusion Criteria

The following are inclusion criteria for prospective study subjects to be confirmed at Visit 1 (Day -14 – Day -2) prior to randomization. The sponsor will not grant any protocol eligibility waivers.

- a. Are ≥ 17 years of age at Visit 1 (Day -14 – Day -2) prior to randomization, of either sex and any race, and scheduled for uncomplicated unilateral cataract surgery (phacoemulsification or extracapsular extraction) with posterior chamber intraocular lens implantation
- b. Signature of the subject or parent(s) or legally authorized representative on the Informed Consent Form (ICF), and when appropriate the minor's assent in accordance with local regulations
- c. Are willing and able to follow all instructions and attend all study visits
- d. Are willing to avoid disallowed medication for the duration of the study
- e. If female is of childbearing potential, agree to and submit a urine sample for pregnancy testing (prior to enrollment and at the end of the study), and use effective contraception for the duration of the study

Male subjects whose female partners are not post-menopausal must agree to one of the following: 1) completely abstain from sexual intercourse, 2) use a barrier method (condoms) with spermicide during sexual intercourse for the duration of the study, 3) provide documentation for having had a vasectomy (with documented infertility)

- f. Have best corrected visual acuity (BCVA) of $+1.0$ log of the minimum angle of resolution (logMAR -Snellen equivalent of 20/200) or better in the fellow eye (non-study eye)
- g. Able to self-instill the IP (or have a caregiver available to instill all doses of the IP, as instructed)
- h. Have an intraocular pressure (IOP) of > 8 mmHg and ≤ 22 mmHg in the surgery eye (study eye)

3.2 Exclusion Criteria

The following are exclusion criteria for prospective study subjects to be confirmed at Visit 1 (Day -14 – Day -2) prior to randomization. The sponsor will not grant any protocol eligibility waivers.

- a. Have a history of Fuchs' dystrophy in the study eye
- b. Have a history of diabetic retinopathy (with visual impairment) and/or previous vitrectomy in the study eye within the last 2 years
- c. Have any sign of iritis or scleritis in the study eye

- d. Have a history of glaucoma surgery in the study eye within the last 2 years
- e. Have an existing diagnosis of severe dry eye in the study eye
- f. Have known hypersensitivity or poor tolerance to any component of the IP or any of the procedural medications such as anesthetic and/or fluorescein drops, dilating drops, etc.
- g. Have an acute ocular infection (bacterial, viral or fungal) or active ocular inflammation in the study eye
- h. Have any extraocular/intraocular inflammation in the study eye noted prior to surgery (blepharitis is allowed if scurf only without any concurrent conjunctivitis or lid erythema/edema) or ongoing, unresolved uveitis
- i. Use of the following disallowed medications within a specified amount of time before surgery:
 - topical, inhaled, or oral corticosteroids within 15 days
 - depot-corticosteroids within 45 days (triamcinolone within 90 days)
 - topical, systemic, or inhaled nonsteroidal anti-inflammatory drugs (NSAIDs) within 1 week (with the exception of low-dose aspirin)
 - ocular or systemic antihistamines, or mast cell stabilizers within 1 week
 - other analgesics and use of acetaminophen (Tylenol[®]) within 48 hours
 - any medication that the investigator feels may interfere with the study parameters
- j. Have any active or chronic/recurrent ocular or systemic disease that is uncontrolled and likely to affect wound healing (e.g., diabetes mellitus, systemic connective tissue disease, severe atopic disease)
- k. Have known blood dyscrasia or bone marrow suppression
- l. Have any active corneal pathology noted in the study eye
- m. Have any intraocular inflammation (cells or flare in anterior chamber) or ocular pain (greater than 0) on the pain scale in either eye
- n. Have had radial keratotomy, corneal transplant, or LASIK in the study eye within the last 2 years
- o. Be currently pregnant, nursing, or planning a pregnancy, or be a woman that has a positive pregnancy test
- p. Are currently suffering from alcohol and/or drug abuse
- q. Prior participation in this study protocol
- r. Prior participation in InSite Vision Protocol C-13-305-002

- s. Have prior (within 30 days of beginning study treatment) or anticipated concurrent use of an investigational drug or device
- t. Have a condition or a situation which, in the investigator's opinion, may put the subject at increased risk, confound study data, or interfere significantly with the subject's study participation
- u. Contact lens wear during the dosing period on Days -1 to Day 14
- v. Use of any medication the investigator feels may interfere with the study parameters

4.0 STUDY TREATMENT AND DRUG/DOSAGE ADMINISTRATION

Subjects will be randomized in a 2:1 ratio to 1 of 2 treatment groups:

1. ISV-305 (0.1% dexamethasone in DuraSite 2) BID (160 subjects)
2. DuraSite 2 Vehicle BID (80 subjects)

One drop of IP will be self-instilled by the subject (or instilled by caregiver) BID, in the surgery eye (study eye) for 16 days: the day prior to surgery, the day of surgery and postoperatively for 14 days.

The study coordinator or investigator will instruct the subjects on the proper administration of their IP.

Subjects (and caregiver as appropriate) will be instructed to bring their pain and dosing diary to each visit for review with site staff and for collection of diary on Day 18 (Visit 6), and to return all bottles of IP on Day 15 (Visit 5) for collection.

5.0 CONTRAINDICATIONS, WARNINGS AND PRECAUTIONS

Contraindications, warning and precautions for ophthalmic dexamethasone as described in the labeling of the approved product Maxidex (0.1% dexamethasone) are presented below.

Use of ophthalmic dexamethasone is contraindicated in epithelial herpes simplex (dendritic keratitis), vaccinia, varicella, and most other viral diseases of the cornea and conjunctiva, tuberculosis of the eye and fungal disease of ocular structures.

Class warnings for corticosteroids such as dexamethasone are well known and state that prolonged use may result in ocular hypertension and/or glaucoma, with damage to the optic nerve, defects in VA and fields of vision, and posterior subcapsular cataract formation. Prolonged use may also suppress the host response and thus increase the hazard of secondary ocular infections. In diseases causing thinning of the cornea or sclera, perforations have been known to occur with the use of topical corticosteroids. In acute purulent conditions of the eye, corticosteroids may mask infection or enhance existing infection. It is recommended that if corticosteroids are used for 10 days or longer, intraocular pressure should be routinely monitored.

The possibility of persistent fungal infections of the cornea should be considered after prolonged corticosteroid dosing.

Subjects are excluded from participating in the study if there is known hypersensitivity or poor tolerance to any component of the IP or any of the procedural medications such as anesthetic and/or fluorescein drops, dilating drops, etc. See Exclusion Criterion f.

6.0 CLINICAL ASSESSMENTS/PROCEDURES

6.1 Schedule of Assessments

The procedures and measurements to be evaluated at each study visit are shown in Table 1: Schedule of Assessments.

Table 1: Schedule of Assessments

Evaluation ¹	Screening/ Randomization Phase	Dosing Phase (16 Days)				Evaluation Phase (15 Days)		
	Visit 1 Day -14 to Day -2	Phone Call Day -3 (±1)	Visit 2 Day 0 (Day of Surgery)	Visit 3 Day 1 (+ 1)	Visit 4 Day 8 (± 1)	Visit 5 Day 15 (+1)	Visit 6 Day 18 (-1/+2)	Visit 7 Day 29 (± 2)
Written Informed Consent	X							
Demographics	X							
Entry Criteria	X							
Medical/Medication History	X							
Urine Pregnancy Test	X							X
Slit Lamp Biomicroscopy ²	X			X	X	X	X	X
Visual Analog Scale	X			X	X	X	X	X
Intraocular Pressure	X			X	X	X	X	X
Best Corrected Visual Acuity	X			X ³	X	X	X	X
Ophthalmoscopy ²	X					X	X ⁵	X ⁵
Confirm and Document Subject Eligibility	X							
Randomization	X							
Dispense IP and Pain/Dosing Diary	X							
Instruct Subject on IP and Dosing/Pain Diary	X							
AE Assessment	X	X	X	X	X	X	X	X
Dosing Reminder Call		X						
Update Concomitant Medications			X	X	X	X	X	X
Review Pain/Dosing Diary			X	X	X	X	X ⁴	X ⁵
Collect IP						X	X ⁵	X ⁵
Collect Pain/Dosing Diary							X	X ⁵
Exit Subject From Study								X

IP = Investigational Product; AE = adverse event; eCRF = electronic case report form

¹All eye exams are to be conducted in the study eye only. The fellow eye (non-study eye) may be examined at the investigators' discretion.

²Performed by a board-certified ophthalmologist.

³A pinhole test may be employed at Day 1 (Visit 3).

⁴Dosing terminates on Day 14. Pain is assessed through the evening of Day 17.

⁵If not completed at previous visit.

Note: Unscheduled visits may occur during the study period. All assessments will be recorded on the eCRF for unscheduled visits, but it is up to the investigator which assessments to conduct. If the subject exits early, all Visit 7 assessments should be conducted, including ophthalmoscopy if not obtained at Day 15 (Visit 5).

